**Version: September 23, 2015**

• **Introduction**

With the epidemic of obesity and type 2 diabetes, patients today frequently require large doses of insulin to achieve optimal glycemic control because of their severe insulin resistance. Such patients often require multiple injections exceeding 100 units at a time, which can cause discomfort and reduced adherence to therapy. Additionally, a large depot of subcutaneous insulin may delay its absorption (1). Because of the higher concentration of U-500 insulin compared to U100 insulin, patients are able to deliver the same amount of insulin in a much smaller volume, increasing patient satisfaction, adherence and improving glycemic control (2).

Despite the increased use of U-500 insulin, the pharmacokinetics and pharmacodynamics have not been well studied, particularly in subjects with diabetes at clinically meaningful doses. De La Pena et al examined the pharmacokinetics and pharmacodynamics of 50 and 100 unit doses of U-500 and U-100 insulin in healthy, non-diabetic obese volunteers (3). They found that the peaks of the concentration and action profiles for U-500 were blunted, and the effect after the peak was prolonged. A limitation of this study is that the doses used were less than what are typically used in clinical practice and time-action profiles may be different at higher doses of U-500 insulin. Additionally, subjects did not have diabetes, and were excluded if they had a BMI >40 (a group that would be more likely to require high dose insulin).

Davidson et al. measured glucose, insulin and C-peptide levels in 9 severely insulin resistant subjects with type 2 diabetes after administration of 100 units of U-500 insulin subcutaneously (4). Insulin concentrations rose by 30 minutes, peaked at 5 hours and remained elevated for at least 7 hours, although the study ended after only 7 hours, so the full duration of the effect is not known.

This paucity of data makes it difficult for clinicians to dose U-500 safely and effectively. A prospective study lasting 24 hours or more is needed to better understand the duration of action of U-500 insulin. In this study, we propose a double blind, crossover euglycemic clamp study in subjects with type 2 diabetes and severe insulin resistance using clinically relevant dosing to determine duration of action and peaks of U-500 insulin. Such information would be of great benefit to clinicians who wish to prescribe U-500 insulin.

• **Objectives**

**Primary Objective:** To determine the duration of action of a single injection of 100 vs. 200 units U-500 insulin in severely insulin resistant patients with type 2 diabetes.

**Secondary Objective:** To determine peak effect of a single injection of 100 vs. 200 units U-500 insulin in severely insulin resistant patients with type 2 diabetes

• **Research design**

*What do we intend to do?*

This will be a single center double blind, crossover study in which subjects will be randomly assigned to receive 100 or 200 units of U500 insulin on two separate occasions separated by a minimum of two weeks. Following U500 administration, euglycemia will be maintained by the variable infusion of dextrose. Our study design is shown in Figure 1.

### *How will we do the work?*

Following ascertainment of eligibility, potential participants will be sent a letter inviting them to learn more about the study. Individuals who contact the study personnel in response to the letter will be screened on the phone and those who meet the inclusion criteria will be invited to come to the research center to be screened in person. At that time the study will be reviewed in detail and informed consent will be obtained. If an HgbA1c has not been measured in the previous month, a sample will be collected for this measure during the screening visit. Subjects will then be scheduled for their first study day and instructed to avoid exercise 48 hours before the study. Directions for how to manage their diabetes medications will be given to the participant. These will be individualized based on the participant's current regimen with the intention to discontinue all medications so none are present at the start of the study.

Subjects will be admitted to Masonic Clinical Research Unit (MCRU) after dinner on the night (between 8-10 PM) before the study. Two catheters will be placed in the arms to establish intravenous access. One will be used for subsequent blood sampling and the other will be used for infusion. Blood glucose will be measured four hours after their dinner and intravenous insulin will be given as necessary to maintain blood glucose between 100-150 mg/dL. Blood sugars will be obtained every 15-60 minutes overnight to ensure the participant remains at target. At 7 AM (time 0) subjects will be given a blinded dose of either 100 or 200 units of U-500 regular insulin subcutaneously. The randomization to dose and the preparation of the injection will be managed by the investigational pharmacy. Blood glucose will be measured starting at time 0 and every 15-60 minutes and variable infusion of 20% dextrose (D20) will be used to maintain euglycemia (100 mg/dL target) according to pre calibrated algorithm. Samples for subsequent measurement of total insulin and c-peptide by Chemiluminescent immunoassay will be collected at time 0 and every 60 minutes. Measurements will be continued until the subject can maintain euglycemia without a glucose infusion for at least 10 hours or until the subject experiences hyperglycemia (BG > 150 mg/dL) for two hours after discontinuation of the glucose infusion irrespective of total duration of glucose infusion. At that point, the catheters will be removed and the subject will be discharged to home. In case of unusual circumstances including high requirements of glucose beyond 24 hours etc, we will assess for recent insulin dosing (< 15 hours as oppose to > 15 hours required per protocol), sulfonylurea screen etc. Carbohydrate free meals will be provided to the participant starting at noon and continued at traditional mealtimes thereafter for the duration of the glucose infusion. Non-caloric decaffeinated beverages will be available as needed. Subjects will be given their home dose of insulin prior to discharge.

Two to four weeks later, the participant will return to complete the second half of the study in which they are given the dose of U500 they did not get at the time of their previous visit. Between visits, subjects will be instructed to go back on their usual diabetes regimen. They will again be instructed to avoid exercise 48 hours before the study and provided with directions for how to manage their diabetes medications in the days immediately before the second visit. These will again be individualized based on the participant's current regimen with the intention to discontinue all medications so none are present at the start of the study. They will again report to the research center after dinner between 8-10 pm and maintained on an insulin drip as necessary to maintain blood glucose between 100-150 mg/dL. At 7 am on the next day the U500 dose will be given and samples will be collected as during the first visit. A glucose infusion will again be given to maintain euglycemia (100 mg/dL) and discontinued using the same plan as for the first visit.

### *What is our study population?*

We will study adults with type 2 diabetes and insulin resistance. Criteria for participation are listed below.

- **Inclusion Criteria**
  - Type 2 diabetes
  - Ages 30-65 years
  - A1c between 7-9.5% within the past month
  - On  $\geq$ 100 units of insulin per day.

- Willing to discontinue oral/injectable non-insulin or insulin hypoglycemic agents for minimum of 15 hours prior to the expected U-500 dose administration.
- Willing to avoid exercise 48 hours prior to study
- Willing to be fasting for up to 24 hours
- BMI between 27 and 38 kg/m^2
- **Exclusion criteria**
  - On systemic corticosteroids in preceding 3 months
  - Heavy alcohol consumption (>21 drinks/week men, >14 drinks/week women)
  - Unwillingness to stop alcohol consumption for 24 hours before each study visit
  - Pregnant or actively trying to conceive
  - Current diagnosis of active infection, cancer (other than basal cell carcinoma), vascular disease, organ failure
  - Current transplant recipient

*How are subjects being selected into the study?*

Potential participants will be recruited from the Diabetes Clinics at the University of Minnesota. They will initially be ascertained for eligibility by review of the electronic medical record or on referral by their personal health care provider.

*What are your treatment groups?*

Each individual will be studied twice, once after the administration of 100 units of U 500 and once after the administration of 200 units of U500. Dosage administration will be in random order.

*What is our assignment strategy?*

The investigational pharmacy at the University of Minnesota will dispense the doses of U 500 insulin and assign the order of administration based on a randomization scheme developed by [name], the biostatistician on the project.

*How many subjects per treatment group?*

We have powered the primary research question using 15 participants, each studied twice as described above. A participant who completes the first dose study but does not return for the second dose study will be replaced.

With 15 subjects (N = 15) completing this cross over study design, we have 85% power using a paired t-test to detect at least a 2 hour difference in the mean duration of action of the 100 vs 200 unit dose of U500 conservatively assuming a within-person correlation of 0.30 (Figure 2). Power will be higher (the detectable difference will be smaller) if the within-person correlation is larger.

*What is the schedule of events?*

Please see figure 1. In random order subjects will be assigned to receive 100 or 200 units of U-500 insulin on two separate occasions separated by a minimum of two weeks. Following U500 administration, euglycemia will be maintained by the variable infusion of dextrose.

• **Concomitant medications**

Subjects will be continued on their non-diabetic medications. Medications used to treat diabetes will be discontinued before the study day. How medications will be discontinued will be individualized based on the participant's current regimen with the intention to discontinue all medications so none are present at the start of

the study. For example, individuals on metformin, sulfonylureas, DPP4Is, GLP-1 agonists will be instructed to not take this drug on the day they will be admitted to the research center.

- **Outcome measures**

**Primary outcome measure:** Duration (in hours) of 20 % dextrose infusion requirement.

**Secondary outcome measure:** 1) Peak 20 % dextrose requirement. 2) Area under the curve (AUC) of 20 % dextrose.

- **Safety measures**

**Investigator related measures:** Our research group has had extensive experience in subject recruitment of patients with diabetes in research studies including GRADE, ACCORD and REWIND. We have performed hundreds of precise clamp studies including euglycemic, hypoglycemic and hyperglycemic. We have a dedicated staff and are well equipped to handle these experiments.

**Subject related measures:** Subjects will be under constant supervision by staff of MCRU overnight during insulin infusion to keep blood glucose within target. U-500 insulin will be handled by Investigational Drug Service (IDS) pharmacy according to institutional policies regarding U-500 regular insulin (attached document: U 500 Insulin Safety Plan, U 500 insulin formulary committee meeting). Pre specified dose of U 500 regular insulin will be calculated, drawn and verified in U-100 insulin syringe at IDS pharmacy according to a conversion chart (attached document: U-500 regular insulin conversion chart). After the administration of insulin, the D20 infusion will be titrated by an experienced member of the group. Subject will remain in the research unit until the subject can maintain euglycemia without a glucose infusion for at least 10 hours or until the subject experiences hyperglycemia (BG > 150 mg/dl) for two hours after discontinuation of the glucose infusion.

- **Sample size computation and power analysis**

We have powered the primary research question using 15 participants, each studied twice as described above. A participant who completes the first dose study but does not return for the second dose study will be replaced. With 15 subjects (N = 15) completing this cross over study design, we have 85% power using a paired t-test to detect at least a 2 hour difference in the mean duration of action of the 100 vs 200 unit dose of U500 conservatively assuming a within-person correlation of 0.30 (Figure 2).

- **Statistical analysis plan**

The duration (in hours) of 20 % dextrose infusion requirement, peak 20 % dextrose requirement , and the AUC of 20 % dextrose will be calculated for each subject after the administration of each of the 100 unit and 200 unit doses of U-500 regular insulin. These measures will then each be compared between doses by paired t-test.

- **Publication strategy**

We intend to submit a report of this work to Diabetes Care and submit an abstract to American Diabetes Association Scientific Sessions in 2015.

- **References**

1. Gagnon-Auger M, du Souich P, Baillargeon JP, Martin E, Brassard P, Menard J, Ardilouze JL. Dose-dependent delay of the hypoglycemic effect of short-acting insulin analogs in obese subjects with type 2 diabetes: a pharmacokinetic and pharmacodynamics study. *Diabetes Care*. 2010 Dec;33(12):2502-7.
2. Dailey AM, Williams S, Taneja D, Tannock LR. Clinical efficacy and patient satisfaction with U-500 insulin

use. *Diabetes Res Clin Pract.* 2010 Jun;88(3):259-64.

- de la Pena A, Riddle M, Morrow LA, Jiang HH, Linnebjerg H, Scott A, Win KM, Hompesch M, Mace KF, Jacobson JG, Jackson JA. Pharmacokinetics and pharmacodynamics of high-dose human regular U-500 insulin versus human regular U-100 insulin in healthy obese subjects. *Diabetes Care.* 2011 Dec;34(12):2496-501.

Figure 1: Study Design

[figure not shown]
[figure not shown]

Figure 2: Power to detect a within-person difference in mean duration of action (hours) for dose 100 units vs. dose 200 units of U500 insulin. Type I error 5% assumed.

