## INFORMATION FOR THE PHYSICIAN

### HUMULIN® R REGULAR U-500 (CONCENTRATED) INSULIN HUMAN INJECTION, USP (rDNA ORIGIN) DESCRIPTION

Humulin R® U-500 is a polypeptide hormone structurally identical to human insulin synthesized through rDNA technology in a special non-disease-producing laboratory strain of Escherichia coli bacteria.

Humulin R U-500 has the empirical formula C257H383N65O77S6 and a molecular weight of 5808.

Humulin R U-500 is a sterile, clear, aqueous and colorless solution that contains human insulin (rDNA origin) 500 units/mL, glycerin 16 mg/mL, metacresol 2.5 mg/mL and zinc oxide to supplement the endogenous zinc to obtain a total zinc content of 0.017 mg/100 units, and water for injection. The pH is 7.0 to 7.8. Sodium hydroxide and/or hydrochloric acid may be added during manufacture to adjust the pH.

Humulin R U-500 is for subcutaneous injection only. It should not be used intravenously or intramuscularly.

Humulin R U-500 contains 500 units of insulin in each milliliter (5-times more concentrated than Humulin R U-100 [see DOSAGE AND ADMINISTRATION]). It also contains 16 mg glycerin, 2.5 mg metacresol as a preservative, and zinc-oxide calculated to supplement endogenous zinc to obtain a total zinc content of 0.017 mg/100 units and water for injection. Sodium hydroxide and/or hydrochloric acid may be added during manufacture to adjust the pH.

Adequate insulin dosage permits patients with diabetes to effectively utilize carbohydrates, proteins and fats. Regardless of dose strength, insulin enables carbohydrate metabolism to occur and thus to prevent the production of ketone bodies by the liver. Some patients might develop severe insulin resistance such that daily doses of several hundred units of insulin or more are required.

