#### DOSAGE AND ADMINISTRATION

Humulin R U-500 is usually given two or three times daily before meals. The dosage and time of Humulin R U-500 should be individualized and determined, based on the physician's advice, in accordance with the needs of the patient. The injection of Humulin R U-500 should be followed by a meal within approximately 30 minutes of administration.

The average range of total daily insulin requirement for maintenance therapy in insulin-treated patients without severe insulin resistance lies between 0.5 and 1.0 unit/kg/day. However, in pre-pubertal children it

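### Do the entry criteria have to guarantee the severe insulin resistance that the objectives name?

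*Combined protocol and SAP*

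**What the plan says.** The last paragraph of the Introduction describes a clamp study "in subjects with type 2 diabetes and severe insulin resistance using clinically relevant dosing". Under Objectives, the primary aim (duration of action) and the secondary aim (peak effect) are both stated "in severely insulin resistant patients with type 2 diabetes".

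The section on the study population opens differently: "We will study adults with type 2 diabetes and insulin resistance". It then refers the reader to the list of criteria. The criteria that bear on resistance are a current dose of at least "100 units of insulin per day", "A1c between 7-9.5% within the past month", and BMI 27 to 38. There is no per-kilogram criterion and no upper dose limit.

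Two statements in the appended product label touch on severity. Its Description says: "Some patients might develop severe insulin resistance such that daily doses of several hundred units of insulin or more are required". Its Dosage and Administration section gives an average: "The average range of total daily insulin requirement for maintenance therapy" "in insulin-treated patients without severe insulin resistance lies between 0.5 and 1.0 unit/kg/day".

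**The concern.** The objectives name one population and the criteria admit what looks like a wider one. The documents' own descriptions of severe resistance also sit above the entry dose. The Introduction speaks of repeated injections, each above 100 units, whereas entry needs 100 units over a whole day. The label's Description speaks of several hundred units daily. A heavy participant at the entry dose would fall inside the label's average range for people without severe resistance.

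The label on the result would be at stake. The Introduction offers the findings to clinicians who prescribe U-500. With 15 participants, each person carries 1/15 (6.7%) of a dose-specific mean. A participant whose duration differs from the others by 2 hours, the difference the trial is powered to detect, moves that mean by 2/15 = 0.13 hours. If several entrants were only moderately resistant, the reported duration and peak would be attached to a description that did not fit them.

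**Working it through.** The plan gives no figure for this point. The one stated calculation, 85% power with 15 completers for a 2-hour difference at within-person correlation 0.30, contains no term for severity. It also cannot be reproduced from the text, because no standard deviation is given and Figure 2 is not shown. Relabelling the same participants leaves it unchanged.

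**Step 1: the entry dose per kilogram.** Inputs: entry dose 100 units/day and BMI 27 to 38 (inclusion criteria); upper end of the average range, 1.0 unit/kg/day (label, Dosage and Administration). Height is not in the documents, so 1.70 m is an assumption.

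- Weight = BMI × height².
- Units/kg/day = 100 / weight, which is 1.0 or less when weight is 100 kg or more.
- Smallest height for 100 kg = √(100 / BMI).

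| BMI | Weight at 1.70 m (kg) | Units/kg/day at 100 units | Smallest height for 1.0 or less (m) |
|---|---|---|---|
| 27 | 78.03 | 1.28 | 1.92 |
| 30 | 86.70 | 1.15 | 1.83 |
| 33 | 95.37 | 1.05 | 1.74 |
| 35 | 101.15 | 0.99 | 1.69 |
| 38 | 109.82 | 0.91 | 1.62 |

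**Step 2: how far above the entry dose the overlap runs.** A dose stays at or below 1.0 unit/kg/day while it does not exceed weight in kilograms. At BMI 38 the upper limit is 38 × 1.70² = 109.8 units/day at 1.70 m, 38 × 1.80² = 123.1 at 1.80 m and 38 × 1.90² = 137.2 at 1.90 m. Put the other way, at BMI 38 a participant on 125 units/day would need to be at least √(125/38) = 1.81 m tall, and one on 150 units/day at least √(150/38) = 1.99 m.

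So the overlap exists. On this yardstick it is limited to heavy participants, mostly with doses not far above 100 units/day.

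**Step 3: whether the yardstick can carry the conclusion.** It cannot, for three reasons.

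- The label gives an average maintenance requirement, not a boundary for severity. The same section goes on to say that requirements may be substantially higher when resistance is due to obesity.
- Current dose is not requirement. Entrants have A1c of at least 7% despite their insulin, and the section on concomitant medications shows that other glucose-lowering drugs may be in use until the study day. Someone at 0.91 unit/kg/day may need more than they take.
- The other dose levels in the attachments (more than 200 units/day in the label, 250 units/day or more in the institutional dosing guideline) say when U-500 is useful or should be considered. They do not define severe resistance.

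**Step 4: what depends on the adjective.** The outcomes are duration, peak and area under the curve of the dextrose infusion. Each participant receives both doses, and the doses are compared by paired t-test. None of these changes if the word severe is kept, removed or defined.

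**The case for a change.** The strongest case for acting is that the difference is plain in the text and cheap to remove. Two sections say severe, the section that decides entry does not, and nothing says that 100 units/day is the trial's working definition. One sentence would settle it, and baseline units/day, units/kg/day and BMI would show readers how resistant the group was.

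The textual difference stands, and so does the statement that the criteria permit severe resistance without ensuring it. The further step, that the objectives claim a population the trial will not have, does not follow. The criteria are introduced as the conditions for taking part, so they can be read as the protocol's practical meaning of the population named in the objectives. Whether that meaning is strict enough is a judgement the documents do not settle. Nor do they say whether the objectives should be fitted to the criteria or the criteria to the objectives.

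The Introduction also counts an earlier study's exclusion of people with BMI above 40 as a limitation, while this trial stops at 38. That concerns how far the results extend by BMI. It is no evidence that entrants lack severe resistance.

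**Conclusion.** No change to the plan follows. Severe is used in the Introduction and Objectives, is absent from the study population section and is defined nowhere. This is a gap in wording that readers and analysts fill sensibly from the listed criteria. A report will state those criteria and would ordinarily tabulate baseline dose and BMI, from which units/kg/day follows.

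No estimate, test, sample size, eligibility rule or safety measure is affected, and the within-person comparison is valid for whoever enrols. The possible overlap with the label's average range needs a weight of 100 kg or more at the entry dose and disappears at BMI 27 for anyone under 1.92 m. How many of the 15 fall in it is unknown and could be none. These sizes rest on assumed heights and on a label average that is not a definition of severity, so they describe the question without showing that the wrong population is enrolled.

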#### CLINICAL PHARMACOLOGY

Regulation of glucose metabolism is the primary activity of insulin. Insulin lowers blood glucose by stimulating peripheral glucose uptake by skeletal muscle and fat, and by inhibiting hepatic glucose production. Insulins inhibit lipolysis, proteolysis, and gluconeogenesis, and enhance protein synthesis and conversion of excess glucose into fat.

Administered insulin, including Humulin R U-500, substitutes for inadequate endogenous insulin secretion and partially corrects the disordered metabolism and inappropriate hyperglycemia of diabetes mellitus, which are caused by either a deficiency or a reduction in the biologic effectiveness of insulin. When administered in appropriate doses at prescribed intervals to patients with diabetes mellitus, Humulin R U-500 restores their ability to metabolize carbohydrates, proteins and fats.

As with all insulin preparations, the duration of action of Humulin R U-500 is dependent on dose, site of injection, blood supply, temperature, and physical activity.

Humulin R U-500 is unmodified by any agent that might prolong its action. Clinical experience has shown that it frequently has time action characteristics reflecting both prandial and basal activity. It takes effect within 30 minutes, has a peak similar to that observed with U-100 regular human insulin and has a relatively long duration of activity following a single dose (up to 24 hours) as compared with U-100 regular insulins. This effect has been credited to the high concentration of the preparation. The time course of action of any insulin may vary considerably in different individuals or at different times in the same individual.

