#### Hypoglycemia

Hypoglycemia is the most common adverse reaction of all insulin therapies, including Humulin R U-500. Severe hypoglycemia may lead to unconsciousness and/or convulsions and may result in temporary or permanent impairment of brain function or death. Severe hypoglycemia requiring the assistance of another person and/or parenteral glucose infusion or glucagon administration has been observed in clinical trials with insulin, including trials with Humulin R U-500.

As with all insulin preparations, the time course of Humulin R U-500 action may vary in different individuals or at different times in the same individual and is dependent on dose, site of injection, blood supply, temperature, and physical activity.

Adjustment of dosage of any insulin may be necessary if patients change their physical activity or their usual meal plan. Insulin requirements may be altered during illness, emotional disturbances, or other stresses. Concomitant oral antidiabetic treatment may need to be adjusted.

Any patient who requires Humulin R U-500 for control of diabetes should be under close observation until appropriate dosage is established. The response will vary among patients. Most patients will require 2 or 3 injections per day.

Insulin resistance, in some patients is transitory; after several weeks or months during which high dosage is required, responsiveness to the pharmacologic effect of insulin may be regained and dosage can be reduced.

The timing of hypoglycemia usually reflects the time-action profile of the administered insulin formulations. Other factors such as changes in food intake (e.g., amount of food or timing of meals), injection site, exercise, and concomitant medications may also alter the risk of hypoglycemia (see PRECAUTIONS, Drug Interactions).

As with all insulins, use caution in patients with hypoglycemia unawareness and in patients who may be predisposed to hypoglycemia (e.g., the pediatric population and patients who fast or have erratic food intake). The patient's ability to concentrate and react may be impaired as a result of hypoglycemia. This may prevent a risk in situations where these abilities are especially important, such as driving or operating other machinery.

Severe hypoglycemia may develop 18 to 24 hours after the original injection of Humulin R U-500.

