- 0. • Humulin R U-500 should look clear and colorless. Do not use Humulin R U-500 if it does not look clear, colorless or has particles in it. Talk with your pharmacist or healthcare provider if you have any questions.
- 0. • Follow your healthcare provider's instructions about how often you should check your blood sugar level for hypoglycemia (too low blood sugar) and hyperglycemia (too high blood sugar).
- 0. • Humulin R U-500 starts working about 30 minutes after injection. The effects of Humulin R U-500 may last up to 24 hours.
- 0. • You should eat a meal within 30 minutes of injecting Humulin R U-500.
- 0. • Choose an injection area (upper arm, abdomen, buttocks, or thigh). Change injection sites within the area you choose for each dose. Do not inject into the exact same spot for each injection. Never inject Humulin R U-500 into a vein or muscle.
- 0. • Inject Humulin R U-500 under your skin (subcutaneous), as shown to you by your healthcare provider.
- 0. • Your healthcare provider should regularly check your diabetes with blood tests, including your blood sugar levels and hemoglobin A1c.
- 0. • If you take too much Humulin R U-500, your blood sugar may fall too low (hypoglycemia). You can treat mild low blood sugar (hypoglycemia) by drinking or eating something sugary right away. Always carry a quick source of sugar, such as hard candy, fruit juice or glucose tablets.
- 0. • Your healthcare provider may prescribe a glucagon emergency kit so that others can give you an injection if your blood sugar becomes too low (hypoglycemic) and you are unable to take sugar by mouth.

There are no special syringes to measure Humulin R U-500. It is important that you use only the syringes that your healthcare provider tells you to use to give your injections of Humulin R U-500. You should use either a U-100 insulin syringe or tuberculin syringe as instructed by your healthcare provider.

- 0. • If you are using U-100 insulin syringes, your healthcare provider should explain how to use this syringe to give the prescribed dose with the unit markings on the syringe.
- 0. • If you are using tuberculin syringes, your healthcare provider should explain how to use this syringe to give the prescribed dose with volume markings on the syringe.

If you do not use the right syringe type, you may take the wrong dose of Humulin R U-500. This can cause you to have too low blood sugar (hypoglycemia) or too high blood sugar (hyperglycemia).

Make sure you know:

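### The 15-hour insulin hold is shorter than the up-to-24-hour U-500 action in the attached label, so a home U-500 user can meet it and start the clamp with home insulin still acting

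*Combined protocol and SAP*

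**What the plan says.** The aim is clear. Under How will we do the work?, the directions for stopping diabetes drugs are individualised "with the intention to discontinue all medications so none are present at the start of the study". The same aim is repeated for the second visit, where participants receive "directions for how to manage their diabetes medications in the days immediately before the second visit", and again under Concomitant medications.

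The number is also clear. The inclusion criterion reads "Willing to discontinue oral/injectable non-insulin or insulin hypoglycemic agents for minimum of 15 hours prior to the expected U-500 dose administration". The study-day description treats 15 hours as the rule: in unusual circumstances, such as a high glucose need beyond 24 hours, "we will assess for recent insulin dosing (< 15 hours as oppose to > 15 hours required per protocol").

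The only worked example of an individualised hold, under Concomitant medications, is that "individuals on metformin, sulfonylureas, DPP4Is, GLP-1 agonists will be instructed to not take this drug on the day they will be admitted". It names no insulin.

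The label attached to the protocol describes, under Clinical Pharmacology, a "relatively long duration of activity following a single dose (up to 24 hours) as compared with U-100 regular insulins". The attached patient information agrees: "The effects of Humulin R U-500 may last up to 24 hours". The label's hypoglycemia precaution adds: "Severe hypoglycemia may develop 18 to 24 hours after the original injection of Humulin R U-500".

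**The concern.** The enforceable number does not secure the stated aim for one kind of participant. Entry requires at least 100 units of insulin a day with no upper limit, and no exclusion mentions U-500. The label describes U-500 as useful above 200 units a day, and recruitment is from diabetes clinics. Someone already taking U-500 can therefore enrol, keep to the 15-hour hold, and receive the study injection while a home dose of the same drug may still be acting.

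The objectives concern a single injection of 100 or 200 units. Carried-in U-500 would be covered by the same dextrose infusion and counted as effect of the study dose. The early part of each profile is the most exposed, which bears on the two secondary outcomes, AUC and peak dextrose requirement.

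**Working it through.** No statistical figure in the plan has to be reproduced here; the check is clock arithmetic.

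Inputs:
- Study injection at 7 AM (How will we do the work?).
- Hold of at least 15 hours (Inclusion Criteria).
- U-500 action of up to 24 hours (attached label and patient information). This is an upper limit, not a typical value.
- Label window for late severe hypoglycemia: 18 to 24 hours after injection.
- Possible home dosing times. The label's usual use is two or three times a day before meals. The attached acute-care dosing guideline gives 8-hourly schedules of 0800-1600-0000 or 0700-1500-2300. Actual home times are an assumption.

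Formulas, with h = hours from the last home dose to 7 AM:
- Maximum overlap = 24 − h, not below zero.
- Late-hypoglycemia window in clamp time = (18 − h) to (24 − h).

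| Home U-500 dose on admission day | h | Maximum overlap (h) | Late window, clamp hours |
|---|---|---|---|
| 4 PM | 15 | 24 − 15 = 9 | 3 to 9 |
| 3 PM | 16 | 24 − 16 = 8 | 2 to 8 |
| Noon | 19 | 24 − 19 = 5 | −1 to 5 |
| 8 AM | 23 | 24 − 23 = 1 | −5 to 1 |
| 7 AM | 24 | 24 − 24 = 0 | −6 to 0 |

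The 4 PM row is the boundary: it meets the inclusion minimum exactly, although the study-day wording asks for more than 15 hours. The 3 PM dose satisfies both. The afternoon doses in the two 8-hourly schedules fall at 4 PM and 3 PM. A mealtime schedule points to the noon or breakfast rows, because a later dinner dose is already barred.

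Bearing on the outcomes:
- **AUC and peak.** In the study of nine severely insulin-resistant patients cited in the Introduction, insulin after 100 units of U-500 peaked at 5 hours. Residue in the first 5 to 9 hours could add to AUC. An effect on peak is less certain, because a noon dose has reached the label's limit by about hour 5.
- **Duration.** In the same study insulin was still elevated when observation ended at 7 hours. Overlap from a noon dose would end before that. Overlap from a 3 or 4 PM dose could run to 8 or 9 hours, but only at the far end of the label's limit. The time at which dextrose stops is therefore probably set mainly by the study dose.
- **Paired comparison.** Equal residue at both visits largely cancels in the difference between doses, but not in each dose's own profile. No section fixes the last-dose time across visits, so unequal residue would add noise.

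**The case against.** The strongest reply is that 15 hours is only a floor. The governing instruction is individualised and aims for no drug on board, with directions covering the days before the visit, so a clinician following it could hold U-500 for longer. That is true, but nothing requires it, and the study-day check treats 15 hours as adequate for insulin: it looks only for dosing inside 15 hours, and only in unusual circumstances. A home U-500 dose 15 to 24 hours earlier would pass.

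Second, the affected group may be empty. The attached acute-care guideline considers U-500 at a total daily dose of 250 units or more, 2.5 times the entry threshold (250/100). This stands, and it limits the weight of the point.

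Third, there are partial safeguards. Glucose is checked every 15 to 60 minutes overnight, intravenous insulin is given only as needed, and total insulin and C-peptide are sampled at time 0. Staff might notice an unusually low overnight insulin need. But the time 0 samples are measured later and do not gate the injection, overnight intravenous insulin complicates their reading, and the Statistical analysis plan makes no baseline adjustment.

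Fourth, the planned analysis consists of paired tests between doses, where common residue largely cancels. This also stands, and it is why the point concerns mainly the absolute profiles and added noise.

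**Conclusion.** The point holds as a conditional design weakness, worth correcting but not of high severity. The one insulin hold stated in hours is up to 9 hours shorter than the U-500 action in the label the protocol attaches. A compliant home U-500 user can therefore start a clamp against the plan's own aim.

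This rests on the label's 24-hour upper limit, on at least one participant using U-500 at home, and on a dose between 7 AM and 4 PM on the admission day. The excess in AUC or peak cannot be sized: the documents give neither the number of such users nor the action left after 15 hours.

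A reader might infer three stronger things that the documents do not support:
- That home insulin will be acting, so AUC and peak are overstated. A limit of up to 24 hours supports only that they could be.
- That the primary comparison of duration is biased. The overlap falls early and is largely shared when timing matches.
- That 0 to 5 hours is the likely overlap. That assumes mealtime dosing, whereas the attached 8-hourly schedules give 8 to 9 hours. Those schedules are institutional and may not describe home use, so no likely range can be stated.

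**What to change.** In the inclusion criteria and the study-day description, keep 15 hours for other agents but require at least 24 hours since the last home U-500 dose, that is, none after 7 AM on the admission day. If needed, bridge with short-acting insulin until the 15-hour cut-off at 4 PM, then use the overnight intravenous insulin already planned.

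At each admission, ask for and record the time and type of the last insulin dose. Apply the 24-hour limit to U-500 in the existing check for recent dosing. Keep last-dose timing the same at both visits. If the hold was missed, rebook, with the second visit kept within its two-to-four-week window.

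The change needs protocol wording and one question per admission, with no new tests, staff or participants. The burden falls on home U-500 users, who would have up to a full day of U-500 doses omitted or replaced before each visit. Someone who doses at 8 AM would be only 23 hours out, so the last U-500 dose becomes the previous evening's. For a last dose at 7 AM, the interval to admission at 8-10 PM is 13 to 15 hours, against 4 to 6 hours from 4 PM. Some risk of higher glucose on the admission day and an occasional rescheduled visit follow.
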